9.7. Baseline Assessments

Routine care involves patients attending a pre-admission surgical clinic usually within 4 weeks of their

surgery. Baseline assessments will therefore be completed within 4 weeks prior to the patient's surgery

date; this can include the day of surgery. Ideally, consent and baseline activities will take place after a

surgery date has been confirmed and as close to surgery as is practicable e.g. at pre-op appointment or

Clinical Research Protocol Template version 15.0

CONFIDENTIAL

© Copyright: The University of Oxford and Oxford University Hospitals NHS Foundation Trust 2019

day of surgery. The assessment involves patient reported questionnaires on shoulder pain and function

and quality of life.

In order to ensure there is an accurate comparison, it is important that the baseline information provided

refers to the patient condition up to a maximum of 8 weeks prior to surgery. Therefore, where a patient's

surgery date is considerably delayed and rescheduled we will seek to complete a repeat Baseline

assessment, if the initial data collection was to fall outside of the 4 week window. This will be

communicated to the patient in the PIS and verbally during recruitment. The Baseline assessment is not

onerous and does not involve an extra visit. We do not anticipate that the 'extra' step of repeating the

baseline assessments, if needed, will result in any negative effect on patient recruitment and will enhance

the reliability of any study findings.

9.8. Operative Assessment

At the time of surgery, the operating surgeon will confirm the diagnosis of a supraspinatus PTT that is more

than half the thickness of the patient's tendon thickness and fulfils the inclusion criteria for randomisation

to ADAR or ADO. Further details of all arthroscopic findings and procedure details will be recorded. This

will include adherence to the randomised allocation, the extent of any concomitant conditions and any

complications.

9.9. Follow up Assessments

9.9.1. Patient Questionnaires

The following questionnaires will be sent to participants at pre-determined timepoints post

randomisation. These will be sent by the central study team and can be completed by post or

online:

Oxford Shoulder Score (OSS)

This patient reported outcome measure (PROM) is a validated questionnaire for

measuring outcomes of rotator cuff surgery in the NHS (24, 25).

EuroQoL EQ-5D-5L

This questionnaire will be completed in order to estimate a health utility index (using UK

population preference weights) and from this estimate quality-adjusted life years for trial-

based economic evaluation (26, 27).

Health Resource Use and patient reported events

Postoperative costs and lost productivity costs attributable to the shoulder condition will

be collected during the follow-up period. Information on outpatient visits, community care

provision, days off work due to their shoulder problem, and patient reported adverse

events will be collected.

Patient Satisfaction and Perception questions

OSS transition and satisfaction questionnaire and a simple Likert scale will be used to

assess participant satisfaction (28, 29).

Reminders will be sent to participants who do not respond to the initial request for follow-up

data within 10 days. If there is still no response, the central study team will use other means of

contact including by telephone. This may be done in conjunction with re-posting of the

questionnaire.; In the case of telephone follow-up, participants will be asked to provide OSS data

as a minimum. Where needed, up to a maximum of 5 attempts will be made.

As required, local research teams will be expected to provide support for follow-up data

collection.

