# 7. STUDY DESIGN

PRoCuRe is a multicentre superiority randomised controlled trial using a two-arm parallel group design with 1:1 allocation ratio and with an internal pilot phase and a Quintet Recruitment Intervention (QRI). Participants will remain unaware (blinded) as to whether they have had their PTT repaired or not.

Participants will be recruited to the study in hospitals across England. The study overall is modelled on participation from 20 centres, but additional sites may be included depending on recruitment rates in the 6-month pilot phase.

Participants (patients) are expected to be enrolled in the study for up to 5 years. During this time, participants will complete questionnaires as per the schedule in Appendix A and flow diagram (Figure 1). They will also be asked to have an MRI scan two years after their surgery. Routine healthcare data will be collected up to five years to assess for any longer- term shoulder diagnoses and healthcare resource use following the repair. Participants will also receive a short questionnaire at 5 years to assess patient reported outcomes, so that long-term clinical and cost effectiveness can be estimated.

[figure not shown]

Figure 1: Patient flow diagram for PRoCuRe

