9.4. Randomisation

Participants will be randomised in theatre after confirmation of a partial tendon tear (PTT) in supraspinatus

that is more than 50% thickness of the tendon. The randomisation will follow a 1:1 allocation ratio and use

a minimisation algorithm; initially simple randomisation seeding will be used and minimisation will also

incorporate a "random twist" element to protect allocation concealment throughout. Randomisation will

be minimised according to age, type of tear and study site.

Randomisation will be performed using a web based automated computer-generated system. The

allocation system will be generated by the trial statistician and will be programmed into the Oxford Clinical

Trials Research Unit (OCTRU) computer randomisation system, Registration/Randomisation and

Management of Product (RRAMP). The research team at each site will conduct the randomisation via

secure logins to the web-based system. An emergency randomisation list prepared by the trial statistician

and held securely by the trial manager will be used if RRAMP is not available.

A member of the clinical research team delegated to treatment allocation (randomising) will enter the

relevant data into the online randomisation system when the patient is in theatre and inform the operating

surgeon of the allocation details. If for some rare reason the patient is not under general anaesthetic, this

will need to be done carefully without revealing the intended treatment to protect the blinding.

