9.5. Blinding and code-breaking

Participants will be blinded to the randomised allocation. It is not possible to blind theatre staff nor the

surgeon. Those in the clinical team and the central trial team will not be blinded to the allocation, so no

code break procedure for clinical care or safety reporting is needed. Post-operative rehabilitation and

exercises will be the same in both groups which means therapists can remain blinded. All participants will

be provided with the same study specific guide to rehabilitation. The participants GP will be notified and

asked not to disclose the treatment allocation to the participant.

24 months after randomisation, patients will be asked which surgical treatment they think they underwent

to assess success of patient blinding.

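### The primary OSS may be collected by telephone by a central team that the protocol describes as unblinded, and no masking of callers is stated

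*Protocol*

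**What the plan says.** **Collection of the OSS (Protocol 9.9.1).** Self-completion is the default: "These will be sent by the central study team and can be completed by post or" online. A reminder goes to those who have not replied within 10 days. After that, "If there is still no response, the central study team will use other means of" contact, with telephone named as one of them and re-posting of the form possible alongside. On the call, "In the case of telephone follow-up, participants will be asked to provide OSS data" as the minimum item. Up to 5 attempts are allowed. Site staff have a looser role: "As required, local research teams will be expected to provide support for follow-up data" collection.

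**Who is blinded (Protocol 7, 9.4, 9.5).** Of participants, section 7 says: "Participants will remain unaware (blinded) as to whether they have had their PTT repaired or not". Of staff, section 9.5 says: "Those in the clinical team and the central trial team will not be blinded to the allocation". Section 9.4 describes how the allocation reaches theatre: "A member of the clinical research team delegated to treatment allocation (randomising) will enter the" data into the online system and then tell the surgeon the result. The check on blinding is a single question: "24 months after randomisation, patients will be asked which surgical treatment they think they underwent".

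**The concern.** The case for this design rests heavily on patient blinding. The justification of treatment arms in section 5 gives secure blinding as a reason for comparing two arthroscopic procedures, and presents the debridement-only control as a way of accounting for placebo effects. Section 9.6.3 repeats the placebo argument.

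A telephone call turns a self-completed score into one elicited by another person. If that person knows the allocation, there are two possible routes to bias. The way items are read, explained or recorded may differ by arm, or the caller may let the allocation slip. Appendix A schedules the OSS at 6, 12 and 24 months, so a slip at 6 or 12 months could also colour a 24-month form that the participant later completes alone.

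The protocol guards other routes. It asks for care if the patient is awake in theatre (9.4), asks GPs not to disclose, notes that therapists can stay blinded (9.5), and sends anonymised MRI scans to independent readers (9.9.2). It states no comparable safeguard for telephone collection of the primary outcome.

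**Working it through.** The point rests on reading sections together. The arithmetic afterwards only shows scale.

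**1. Reading the sections side by side**
- Section 9.9.1: the central study team contacts non-responders and asks for the OSS by telephone.
- Section 9.5: the central trial team is not blinded. The two sections use slightly different names for the team, but the protocol defines no separate masked group.
- Section 9.8 has procedure details and adherence to allocation recorded, and section 13.3 has the central trial team validate and query site-entered data. Allocation therefore lies within that team's ordinary work.
- Sections 9.5 and 9.9.1 contain no statement on masked callers, a call script, or recording how the OSS was completed.
- The treatment-guess question at 24 months can partly detect disclosure. It cannot detect a caller's influence on answers.

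**2. The plan's own figure (section 11.3)**
Inputs: target difference 4, SD 9, two-sided 5%, power 90%.
- Normal approximation: n = 2 × (1.960 + 1.282)² × 9² / 4² = 106.4, so 107 per group.
- Noncentral t: 107 gives power 0.899 and 108 gives 0.902, so 108 per group, as stated.
- 216 / 0.80 = 270 and 270 / 0.70 = 385.7, rounded up to 386, as stated.

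The sample size reproduces, and the point does not depend on it.

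**3. Scale, on assumed inputs only**
Let f be the share of OSS values taken by telephone, and b the between-arm shift caused by callers within that share. The protocol gives neither. The shift in the overall difference is f × b. The standard error at 108 per group is 9 × √(2/108) = 1.22. With a shift always in one direction, the normal approximation gives:

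| f (assumed) | b (assumed) | f × b | % of 4-point target | Two-sided type I error | Power if the shift dilutes a true 4-point effect |
|---|---|---|---|---|---|
| 0 | – | 0 | 0 | 5.0% | 90.4% |
| 5% | 1 | 0.05 | 1.25 | 5.0% | 89.7% |
| 10% | 2 | 0.2 | 5 | 5.3% | 87.3% |
| 20% | 2 | 0.4 | 10 | 6.2% | 83.6% |
| 30% | 4 | 1.2 | 30 | 16.5% | 62.8% |

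The last row is an extreme: b = 4 supposes that callers alone create the whole target difference among those telephoned. Callers who lean in opposite directions would partly cancel.

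**The case against.** **The respondent is blinded.** The OSS is a patient-reported score, and an unblinded caller is not the rater. Bias needs either leading that differs by arm or a disclosure, and the documents show neither. This stands. A reader might infer that blinding of the primary outcome is broken; the text supports only that a route is left open.

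**Not every non-responder is affected.** Telephone follows a mailing and a reminder, is one of several means of contact, and may accompany a re-posted form. It would be wrong to infer that all who miss the first mailing give the OSS to an unblinded caller. The affected share is unknown.

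**Local staff.** A reader might infer that site staff who know the allocation administer the OSS. Section 9.9.1 gives them only unspecified support, and the protocol does not say that every local researcher is unblinded. The central-team point stands without this.

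**The numbers are not evidence.** This also stands. Both f and b are assumed, and the table should carry no weight as an estimate.

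**Detail belongs elsewhere.** Scripts and data fields can sit in working documents, and an analysis by mode can sit in the statistical analysis plan, so their absence from the protocol is not in itself a fault. The blinding status of the callers is different, because section 9.5 makes a positive statement about it.

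**Masked callers may be scarce.** If fewer calls were made, primary data could be lost, and section 11.4 uses no imputation in the main analysis. This is a fair objection and calls for a fallback.

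**Conclusion.** The point holds in a limited form. As written, the protocol lets a team it describes as unblinded elicit part of the primary outcome by telephone, and it states no safeguard for those calls. This leaves interviewer influence and accidental disclosure possible, in either direction, for an unknown share of OSS values.

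The conclusion rests on the central study team and the central trial team being the same, or at least not separated by masking; nothing in the protocol separates them. The size of any bias cannot be derived from the protocol. Neither a demonstrated bias nor administration of the OSS by unblinded site staff is supported by the text. The sample size needs no change. This is a worthwhile, inexpensive improvement and not a flaw that threatens the trial.

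**What to change.** - In sections 9.5 and 9.9.1, state that telephone OSS is taken, where possible, by existing trial-office staff without access to allocation or theatre data, who read the OSS items verbatim from a fixed script.
- Apply the same condition to any local staff who help to collect the OSS.
- Record the mode of completion and whether the caller was masked.
- Examine the primary result by mode of completion in a sensitivity analysis.
- If no masked caller is available, keep the scripted call and flag the value, so that primary data are not lost.

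**Cost:** some reassignment of calls within the existing team, access restrictions for those callers, a short script, and one or two extra data fields. Telephone follow-up itself is kept.

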9.9.2. MRI Assessment

For randomised participants, an MRI is required two years after surgery to evaluate the tendon

appearance and to assess if a FTT has developed. This assessment will determine the structural

outcome of the surgical procedures. Identification of progression to FTT over time will indicate

the mechanical failure in the surgical repair group, or progression of unrepaired PTTs to FTTs, as

well as providing insight into whether progression to FTTs correlates to poorer clinical outcomes.

Standard MRI images will be taken at the participants' local hospital and performed according to

the NHS Trust's policies and procedures. An anonymised copy of the scan will be collected

centrally and reported by independent radiology experts to evaluate for any FTTs. This method of

assessment has been used in previous trials of this patient population (3).

Sites will refer to study specific instructions on the transfer of MRI images. Where available, de-

identified MRI scans will be transferred using the NHS trust secure Image Exchange Portal (IEP). If

IEP is not available at a recruiting centre, the anonymised image will be copied to CD and sent to

the PRoCuRe office, Oxford, where the image will be uploaded to the OUH NHS Trust PACS system.

Staff at site will be responsible for removing identifiable data from the image and labelling with

Clinical Research Protocol Template version 15.0

the relevant study ID prior to transfer. Sites will follow local Information Governance process to

ensure patient confidentiality.

MRI is commonly used every day within the NHS and all hospital Trusts have robust policies and

procedures in place to ensure patient safety. Many patients will have undergone such an MRI

scan(s) prior to their participation in the PRoCuRe study.

Participating sites will assume responsibility for coordinating the follow up MRI appointment for

their randomised participants. The scan should take place 24 months post-randomisation (+/- 2

weeks) and the scan image transferred to Oxford as soon as possible after.

9.9.3. Long Term Follow Up

To obtain long term data about randomised participants beyond the 24-month timepoint, data

will be collected via Hospital Episode Statistics (HES) data from hospitals in England, and a simple

questionnaire will be sent to participants, involving questions on patient satisfaction, and

perception of their treatment. A repeat OSS and EQ5D will also be collected.

HES data will be collected for the non-randomised participants; this group will not be asked to

complete a questionnaire at 5 years post-surgery.

HES Data - Routinely-collected data will be used to determine re-operation rates on trial

participants up to five years following initial surgery. A bespoke HES extract provided by

NHS Digital and linked to the Office of National Statistics data is required. This will include

all events and outcomes associated with any further shoulder surgery using a pre-agreed

list of procedure (OPCS 4.7) and clinical diagnosis (ICD10) codes and including but not

limited to: primary rotator cuff repair, revision rotator cuff repair, augmented rotator cuff

repair, arthroscopic debridement, biceps tenotomy, shoulder replacement. Consent will

be collected from patients during recruitment to use their HES data in this way.

9.10. Tissue Samples

All participants will be invited to consent to providing a very small sample of tendon tissue that is otherwise

usually routinely removed and discarded during debridement or repair preparation; it is possible to decline

and remain a participant in the study. For all participants who consent to provide a sample, tissue will only

be collected from those who are eligible for randomisation. Information relating to tissue sampling will be

included in the PIS.

Once patients are deemed to have the appropriate PTT and eligible for randomisation then a tissue sample

can be considered. Tissue will be collected from the patients who either undergo a tear debridement or

those that undergo a takedown repair and have consented to provide a sample. Only the small amount

tissue that would otherwise be debrided and discarded during the procedure will be collected. The volume

of tissue collected would be around the size of a grain of rice.

The tissue samples will be analysed by a variety of laboratory techniques to allow us to characterise how

the diseased tissue looks at a cellular and molecular level. Examples of techniques to be used include

transcriptomic, metabolomic and proteomic analysis and subsequent validation using RT-qPCR, FACs and

immunostaining. These methods will allow us to identify cells and molecules characteristic of disease and

that may predict outcome from surgery. We will also be able to compare data to healthy tendon samples

we have collected from other separate studies. Some tendon samples will be processed so that we can

study the cells from the tissues in the laboratory and test which surgical biomaterials or drugs best change

their behaviour so that they look like healthy tendons - this will identify promising treatments for partial

rotator cuff tears.

The tissue samples are small and each sample will only be processed for one laboratory application. The

samples will be transferred from the clinical collection sites in appropriate and safe containers and

received and stored in a secure laboratory area within The Botnar Research Centre in accordance with

Human Tissue Authority (HTA) guidance. Access will be restricted to authorised personnel associated with

the study.

9.11. Early Discontinuation/Withdrawal of Participants

During the course of the study a participant may, where it is still possible, choose to withdraw early from

the randomised intervention or other trial procedures at any time. This may happen for several reasons,

including but not limited to:

• Investigator decision

o Ineligibility (either arising during the study or retrospectively, having been

overlooked at screening)

o Other clinical reasoning

o Significant protocol deviation

o Significant non-compliance with treatment regimen or study requirements

• Participant decision

The occurrence of what the participant perceives as an intolerable adverse event

Inability to comply with study procedures

The type of withdrawal and reason for withdrawal will be recorded in the relevant Case Report Form (CRF).

If the participant is withdrawn due to an adverse event, the Investigator will arrange follow up until the

event has resolved or stabilised. Withdrawal (from any or all aspects of the study) will managed via the

Oxford office.

Participants may decide any of the following types of withdrawal:

Withdrawal from follow up MRI assessment but willing to complete questionnaires at home

Withdrawal from follow up MRI assessment and completing questionnaires, but willing for the

study team to access medical records and any relevant hospital data that is recorded as part of

routine care. These patients may also be willing to be followed up via HES

Withdrawal from all follow-up, but willing for data collected up to the point of withdrawal to be

included in the final study analysis

Complete withdrawal, with data collected not being used in the final study analysis. Where

available, this will include tissue samples and/or audio-recordings that are still identifiable. (There

are limits to this, for example when data has already been integrated into interim results)

All patients who withdraw from the study will continue to receive routine clinical care.

Participants will not be replaced, as withdrawal and loss to follow-up has been accounted for in the

estimated sample size. Analysis will be performed as per intention-to-treat, irrespective of compliance

with treatment allocation.

9.12. Definition of End of Study

The end of the initial follow-up is defined as the final participant assessment at 24 months, and after all

data has been entered and queries resolve. The end of the trial is defined as 3 years after this point when

all longer term (5 year) follow-up data has been collected and queries resolved.

10. SAFETY REPORTING

The study involves no additional risks to participants beyond those of routine standard care. Participants

will be informed of the standard risks associated with the anaesthetic and surgery.

Clinical Research Protocol Template version 15.0

CONFIDENTIAL

© Copyright: The University of Oxford and Oxford University Hospitals NHS Foundation Trust 2019

Adverse Events (AEs)

Complications (adverse events) that the clinicians deem associated with the patient population and the

trial treatments will be collected via the REDCap database. Examples of expected adverse events that can

occur with this type of surgery include, but are not limited to:

o Infection

Frozen Shoulder

Tendon Re-tear

Ongoing Pain with minimal clinical improvement

Further shoulder surgery (requiring inpatient hospitalisation)

Recurrence of same problem

Conversion to open surgery

o Poor movement

Cartilage damage

o Future arthritis

o Instrument breakage

Nerve or vessel injury

Fracture needing further surgery

Scar tenderness

o Bleeding

Complications of anaesthetic and nerve block

Sites will use the Complications eCRF to record information on AEs occurring from the day of surgery to 24

months post-randomisation; sites will also conduct a notes review at the 24 months post-randomisation

timepoint. Information on complications experienced by randomised participants will also be solicited

from the follow-up questionnaires up to 24 months. Complications occurring during surgery (randomised

participants) will be collected from sites via the theatre form eCRF.

Adverse events experienced by randomised participants will be periodically reviewed by the Data Safety

Monitoring Committee (DSMC) and any unusual increased patterns of serious adverse events (i.e.

complications defined as serious) compared to what is expected for such patients and interventions will

be notified to the Research Ethics Committee (REC).

Serious Adverse Events (SAEs)

SAEs occurring to a randomised participant, from surgery and up to 24 months post-randomisation,

clinically judged by the PI as being related to the intervention will be reported via the PRoCuRe SAE form

for review by the nominated person. All deaths, related or unrelated, will be reported. Sites will report

any events meeting these criteria to the central study team within 24 hours of the PI becoming aware of

the event. The central study team will review the submission reports of related and unexpected SAEs will

be submitted within 15 working days of the Chief Investigator becoming aware of the event.

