10.1. Definition of Serious Adverse Events

A serious adverse event is any untoward medical occurrence that:

results in death

is life-threatening

requires inpatient hospitalisation or prolongation of existing hospitalisation

· results in persistent or significant disability/incapacity

consists of a congenital anomaly or birth defect

Other 'important medical events' may also be considered a serious adverse event when, based upon

appropriate medical judgement, the event may jeopardise the participant and may require medical or

surgical intervention to prevent one of the outcomes listed above.

NOTE: The term "life-threatening" in the definition of "serious" refers to an event in which the participant

was at risk of death at the time of the event; it does not refer to an event which hypothetically might have

caused death if it were more severe.

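### Section 10 lets unblinded clinicians' judgement of cause decide which post-operative harms sites must record; the clearest gap is an unlisted, non-fatal SAE judged unrelated (minor, cheap to close)

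*Protocol*

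**What the plan says.** Protocol section 10 sets up several routes for harms in randomised participants.

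- **SAE form.** From surgery to 24 months, a non-fatal SAE is reported within 24 hours if it is "clinically judged by the PI as being related to the intervention will be reported via the PRoCuRe SAE form". All deaths are reported, related or not.
- **Complications eCRF.** Sites enter adverse events from the day of surgery to 24 months and review the notes at 24 months. The events in scope are "Complications (adverse events) that the clinicians deem associated with the patient population and the" trial treatments. An open-ended list of 16 example types follows, including "Further shoulder surgery (requiring inpatient hospitalisation)".
- **Theatre form.** Complications during surgery (randomised "participants) will be collected from sites via the theatre form eCRF", with no relatedness condition stated.
- **Participants.** Complications are also solicited "from the follow-up questionnaires up to 24 months".

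Section 10.1 counts as serious any event that "requires inpatient hospitalisation or prolongation of existing hospitalisation", among other criteria. The DSMC reviews adverse events periodically, and the REC is told of unusual patterns of SAEs (that is, "complications defined as serious) compared to what is expected for such patients and interventions will" be notified).

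On blinding, section 9.5 says: "Those in the clinical team and the central trial team will not be blinded to the allocation". Section 11.4 groups complications and further surgery by treatment received and also summarises them as randomised.

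**The concern.** ADAR is ADO plus a tendon repair, so any extra harm from the repair is a safety question for this trial. A fair comparison of harms needs a recording rule that works the same way in both arms. If recording depends on what the clinician believes caused the event, and the clinician knows whether a repair was done, the same event can be attributed to the operation in one arm and to the underlying condition in the other. It would then be recorded unequally. The DSMC and REC safeguards in section 10 work from recorded events. The protocol states neither a blinded assessment of relatedness nor a rule that sites record serious events whatever their cause.

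**Working it through.** The protocol gives no complication rates and no recording probabilities, so there is no stated safety figure to reproduce. The check has two parts: tracing each kind of event through the forms, and giving a scale for a few missed events.

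**1. Which route must capture which event (sections 9.9.2, 9.9.3, 10, 10.1 and 12.4)**

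| Event in a randomised participant, to 24 months | SAE form | Complications eCRF | Other source |
|---|---|---|---|
| Death, any cause | Required | – | – |
| Complication during surgery | If serious and judged related | – | Theatre form, no stated relatedness condition |
| Listed type, serious, judged related | Required | Yes | Questionnaire; HES or MRI for some |
| Listed type, serious, judged unrelated | Not required | Yes if the wording means types; doubtful if applied case by case | Questionnaire; HES or MRI for some |
| Unlisted, serious, non-fatal, judged related | Required | Yes | Questionnaire |
| Unlisted, serious, non-fatal, judged unrelated | Not required | Not required on either reading | Questionnaire; HES only if the admission counts as related |

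Only the last row has no required site record. An example is an admission in the weeks after surgery that the PI puts down to a pre-existing illness. The fourth row is at risk only on the less natural reading of the eCRF wording.

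**2. How far the 16 listed types are covered elsewhere (this review's own classification)**

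- Wholly or often intra-operative, so able to reach the theatre form (6): conversion to open surgery, cartilage damage, instrument breakage, nerve or vessel injury, bleeding, anaesthetic and nerve block complications.
- At least partly measured by another outcome source (6): tendon re-tear (central MRI); ongoing pain, recurrence and poor movement (OSS); further shoulder surgery and fracture needing surgery (HES, if on the agreed code list).
- Resting on site recording and questionnaires (4): infection, frozen shoulder, scar tenderness, future arthritis.

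6 + 6 + 4 = 16. The split is debatable. For example, an infection needing admission may also appear in HES.

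**3. Scale**

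Inputs: section 11.3 gives 108 per group before attrition and 20% attrition, and 108/0.8 = 135 per group, as stated. The true event rate p is an assumption, shown from 5% to 20%.

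- One unrecorded event moves its arm's rate by 1/135 = 0.74 percentage points.
- The standard error (SE) of the difference between arms is √(2p(1−p)/135):
  - p = 5%: √(0.095/135) = 2.65 points, × 135 = 3.6 events
  - p = 10%: √(0.18/135) = 3.65 points, × 135 = 4.9 events
  - p = 20%: √(0.32/135) = 4.87 points, × 135 = 6.6 events

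One or two unrecorded events in one arm are therefore well inside chance variation.

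As an illustration with invented recording rates, take equal true rates of 10% (13.5 events per arm):

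- 90% v 70% recorded gives 12.15 v 9.45 events. The apparent risk ratio is 0.9/0.7 = 1.29, and the difference of 2.7 events is below one SE.
- 90% v 50% recorded gives 12.15 v 6.75 events. The ratio is 1.80, and the difference of 5.4 events is about 1.1 SE.

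Nothing in the protocol suggests that recording would differ this much.

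**The case against.** The strongest reply is that the SAE form is an urgent-reporting tool and not the harms dataset. Section 10 gives the DSMC adverse events generally and describes the SAE patterns sent to the REC as serious complications, so both draw on the Complications eCRF. The eCRF wording leads straight into an open-ended list that includes persistent pain, recurrence and poor movement. A causal filter would tend to exclude those items, so the phrase is best read as naming types of event. This reply largely stands. It leaves the text silent on how an unlisted event is handled once it is judged unrelated.

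A reader might infer three stronger things, none of which the protocol supports.

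- *That further surgery can be lost through attribution to the tear.* It is a listed adverse event, so on the natural reading the attribution affects only whether the urgent form is filed. HES also captures re-operations.
- *That an event a site does not record is gone for good.* Blinded participants are asked about complications in the follow-up questionnaires. HES follows randomised participants from randomisation (section 12.4), so it includes the first 24 months, although it is analysed separately and after the 24-month main analysis (section 11.1).
- *That the comparison of harms is biased towards one arm.* The protocol gives no basis for a direction or a size.

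Limiting expedited reporting to related events and deaths is not disputed here. How the safety tables are laid out is a matter for the SAP. The listed term tendon re-tear fits a repaired tendon better than an unrepaired one, but this matters little because central MRI looks for full-thickness tears in both arms (section 9.9.2).

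**Conclusion.** The point holds as a minor one. As written, section 10 allows an unblinded judgement of cause to act as a gate on site-recorded post-operative harms. It leaves one clear gap, the unlisted, non-fatal SAE judged unrelated. It also leaves one ambiguity, whether the eCRF wording names types of event or sets a test for each case. The exposure is small and of unknown direction, and it does not reach the OSS or the primary analysis. This rests on reading the eCRF wording as describing types. If sites applied it case by case, some listed events, chiefly those without another outcome source, would also depend on an unblinded opinion. The point is worth acting on because the correction is cheap, not because material bias has been shown.

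**What to change.** Add to section 10 that two groups of events in a randomised participant up to 24 months are recorded on the existing Complications eCRF whatever their judged cause: every occurrence of an event type listed in section 10, and every event meeting the section 10.1 definition. Have both groups checked at the existing 24-month notes review. Put the PI's opinion on relatedness in a separate field, so that it describes an event and does not decide whether it is recorded. Keep 24-hour SAE-form reporting and expedited reporting limited to related events and deaths, as now.

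The cost is a change to protocol and eCRF wording and one added field. Sites would enter somewhat more events, including some unrelated to the shoulder, partly from a notes review they already carry out. No new visit, form or expedited report is needed. The change would not remove differences in how closely unblinded staff look for events.
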